3.1.2 INDIVIDUAL LEVEL REMINDERS

After the initial two-week roll-out/administration period, follow-up emails will be sent out by the research team to patients at treatment practices whose doctors have placed blood glucose flowsheet orders. Patients will be assigned at the individual level to one of four reminder treatment conditions, which will be administered by the research team. The number of reminder conditions may be reduced (to 2 or 3 instead of 4) depending on the rate of flowsheet orders by physicians to preserve statistical power. Assignment to any of these treatments will not preclude or provide guidelines for other communication between providers and patients (e.g. providers are free to send out their own reminders or messaging regardless of patient assignment to treatment group). The four reminder treatment conditions are described below:

(1) No additional reminders from research group

(2) Standard secure message reminder, addressed from Inova Medical Group, sent every two weeks during 12 week implementation period. Draft text below:

*Dear [Patient],
Don't forget to track your blood glucose through MyChart! Keeping track of your blood glucose can help you manage your diabetes and reduce your chances for developing complications like heart disease, kidney damage and eye damage.
Sincerely,
Inova Medical Group*

(3) Secure message reminder with chance to receive gift card, addressed from Inova, sent every two weeks during 12 week implementation period. Draft text below:

*Dear [Patient],
You have been chosen for a special program to help you get started tracking your blood glucose through MyChart. For each day that you track your blood glucose on MyChart through [DATE], you will be*

entered to receive one of fifty \$50 gift cards to Amazon. You'll be sent a secure message through MyChart after [DATE] if you've been selected to receive a gift card. Keeping track of your blood glucose can help you manage your diabetes and reduce your chances for developing complications like heart disease, kidney damage and eye damage.

Sincerely,

Inova Medical Group

(4) Secure message reminder, addressed from primary care doctor, sent every two weeks during 12 week implementation period. Draft text below:

Dear [Patient],

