3.3 Randomization

Provider-side treatments will be cluster randomized at the practice level. Randomization will stratify across practices by number of diabetic patients (cluster size), and will be conducted using a random number generator at the outset of the study. Reminder messaging treatments will be assigned alphabetically by first two letters of patient last name, as it is logistically infeasible to do individual level patient messaging without sorting on an existing field in the patient's EHR. There are some concerns that ethnicity could correlate with assignment based on last name spelling, so this form of assignment is "pseudo-random". However, the patient's race/ethnicity recorded in the medical record will be controlled for in the analysis. Causal interpretation of the results of the reminder messaging portion of the experiment will thus require the assumption that grouped last name spelling is not independently related to likelihood of flowsheet adoption.

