4.1 Sample Size

Non-pregnant adult patients of Inova primary care physicians with a current diabetes mellitus diagnosis and active MyChart account at time of treatment administration will be included in the study. The estimated number of patients is around 7200, from 71 primary care physicians across 24 selected Inova primary care practices.

Power Calculations

Power calculations were performed using the “clustersampsi” command in Stata. Knowledge of available sample and estimates/assumptions of control outcome mean, variance, and intraclass correlation were used to calculate a minimum detectable effect size for the key outcomes of flowsheet adoption (extensive margin, dichotomous rate of adoption) and changes in mean A1c.

Flowsheet Adoption: Practice Level Treatment-Control Comparison

Sample Size: 7200

Number of Treatment Arms: 2

Number of Clusters: 24

Assumed Control Adoption Rate: 2%

Assumed Intra-Cluster Correlation (within practices): 0.1

Minimum Detectable Effect: **9.5 percentage point increase in flowsheet orders**

Mean HbA1c: Practice Level Treatment Control Comparison

Sample Size: 7200

Number of Treatment Arms: 2

Number of Clusters: 24

Assumed Control HbA1c Mean: 6.74

Assumed Control HbA1c Standard Deviation: 1.39

Assumed Intra-Cluster Correlation (within practices): 0.07

Assumed Baseline Correlation: 0.80

ITT Minimum Detectable Effect: **0.27 change in A1c**

Flowsheet Adoption: Individual Level Comparison between Messaging Assignment Groups in Treatment Practices

Sample Size: 3600

Number of Arms (including no reminder): 4

Assumed No Reminder Adoption Rate: 20%

Minimum Detectable Effect: **5.5 percentage point increase in use of flowsheets when compared to no reminder**

Justification

The sample size represents the entire population of Inova primary care patients with diabetes who have active MyChart accounts and are therefore able to access the blood glucose tracking feature. The minimum detectable effects resulting from power calculations above are in-line with similar studies cited in the protocol background. Metastudy reviews of the effect of self monitoring of blood glucose found a 0.33 point change in A1c.

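### Reminder arms are described and powered as individual-level but allocated by surname letters, with no random step, no matching variance method and an unclear denominator

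*Combined protocol and SAP*

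**What the plan says.** Section 3.1.2 states that "Patients will be assigned at the individual level to one of four reminder treatment conditions". It sends the reminders to treatment-practice patients for whom a flowsheet order exists, and allows the four conditions to be cut to two or three if orders are few. Section 4.1 heads the matching power calculation "Individual Level Comparison between Messaging Assignment Groups in Treatment Practices". Its inputs are 3,600 patients, four arms and a 20% no-reminder adoption rate, with no intra-cluster correlation, and it reports a "5.5 percentage point increase in use of flowsheets when compared to no reminder".

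Section 3.3 gives the allocation rule: "Reminder messaging treatments will be assigned alphabetically by first two letters of patient last name". The practice-level randomisation in the same section "will be conducted using a random number generator at the outset of the study"; nothing similar is said for reminders. The section labels the scheme pseudo-random and gives a logistical reason: messages can only be sent by sorting on an existing record field. It raises a possible link with ethnicity, promises that "race/ethnicity recorded in the medical record will be controlled for in the analysis", and says that a causal reading needs "the assumption that grouped last name spelling is not independently related to likelihood of flowsheet adoption".

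Section 3.4 compares individuals across reminder groups within treatment practices. Section 4.2 clusters standard errors by practice for the practice-level comparisons and gives no variance method for the reminder comparisons.

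**The concern.** There are three linked gaps.

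1. **Allocation.** The unit assigned is a surname group, not a patient, and no chance mechanism is described. The rule as worded allows anything from scattered prefixes to four consecutive alphabetic blocks. Adjusting for race/ethnicity removes only the part of a surname correlation that the recorded categories capture, and analysis version (a) in Section 4.2 has no covariates at all. The stated assumption covers flowsheet adoption only. Section 3.4 uses the same groups for A1c, doctor-patient contacts and treatment changes, by intent to treat and treatment on the treated, so the assumption must hold there too.
2. **Variance.** The power calculation treats 3,600 patients as independent, and no planned standard error reflects allocation by surname group.
3. **Denominator.** By Section 1.3, a patient cannot use the flowsheet without an order, and reminders go only to patients with orders. Yet 3,600 is half of 7,200, that is, every patient in the treatment practices. Section 6.2 gives a further base: a quarter of the diabetes patients in 10 practices. It is not stated whether patients without orders are analysed, or over whom the 20% is taken.

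At stake are the causal reading of the reminder results and the meaning of the 5.5 points.

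**Working it through.** **Inputs from Section 4.1:** N = 3,600, four arms, no-reminder rate p₁ = 0.20, stated effect 5.5 points. **Assumed, because not stated:** equal arms, two-sided α = 0.05, 80% power.

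**Step 1. Reproduce the plan's figure.** With d = p₂ − p₁ and p̄ = (p₁ + p₂)/2, solve

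n = [1.96·√(2p̄(1−p̄)) + 0.8416·√(p₁(1−p₁) + p₂(1−p₂))]² / d²

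for n = 3,600/4 = 900. At p₂ = 0.2553, the bracket is 1.96 × 0.5930 + 0.8416 × 0.5917 = 1.660. Its square is 2.756, and √(2.756/900) = 0.0553. The detectable effect is **5.53 points**, so the plan's figure is right for independent patients with a design effect of 1.

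**Step 2. Other patient and arm counts, same formula.**

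| Setting | n per arm | Detectable effect (points) |
|---|---|---|
| 3,600 in three arms | 1,200 | 4.76 |
| 3,600 in two arms | 1,800 | 3.86 |
| 4,500 (half of the 9,000 in Section 2.4) in four arms | 1,125 | 4.93 |
| 10 practices (Section 6.2) at the average 7,200/24 = 300 patients, four arms | 750 | 6.09 |

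So 5.5 is not a bound in either direction.

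**Step 3. Order rate f.** The documents give none; I take 75%, 50% and 25%.

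(a) Only ordered patients analysed, 20% among them, n per arm = 3,600f/arms:

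| Arms | f = 75% | f = 50% | f = 25% |
|---|---|---|---|
| 4 | 6.43 | 7.96 | 11.52 |
| 3 | 5.53 | 6.84 | 9.88 |
| 2 | 4.48 | 5.53 | 7.96 |

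(b) All 3,600 analysed in four arms, with 20% the rate among ordered patients. The overall base rate is 0.20f (0.15, 0.10, 0.05). The detectable effect is 5.02, 4.31 or 3.29 points overall. Divided by f, that is 6.69, 8.63 or 13.15 points among ordered patients, the only ones reminded.

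(c) All 3,600 analysed, with 20% the rate over all of them: 5.53 at any f.

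**Step 4. Surname clustering with scattered prefixes.** Assumed: 200 prefixes, so m = 3,600/200 = 18; cluster-size CV = 1; ICC 0.001 to 0.005. The formulas are

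- design effect DE = 1 + ((CV² + 1)m − 1)·ICC = 1 + 35·ICC;
- detectable effect from Step 1 with n = 900/DE;
- type I error of an unclustered test = 2(1 − Φ(1.96/√DE));
- between-prefix SD = √(ICC × 0.2 × 0.8).

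| ICC | Between-prefix SD (points) | DE | Detectable effect (points) | Unclustered type I error |
|---|---|---|---|---|
| 0.001 | 1.26 | 1.035 | 5.63 | 5.4% |
| 0.002 | 1.79 | 1.070 | 5.73 | 5.8% |
| 0.005 | 2.83 | 1.175 | 6.02 | 7.1% |

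With 100 units instead of 200 (m = 36, DE = 1 + 71·ICC), the detectable effects are 5.74, 5.93 and 6.49 points.

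**Step 5. One alphabetic block per arm.** Each arm then has a single unit. A difference in adoption between blocks of surnames cannot be told apart from a reminder effect, so there is no variance correction to compute.

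**The case against.** The strongest reply is that this is a disclosed trade-off. Section 3.3 states the surname rule, its reason, the ethnicity concern, the planned adjustment and the assumption, so nobody is misled about the method. Individual-level may be meant only as the contrast to practice-level. The documents do not say whether the messaging system can send by scattered prefixes, so the better map may not be available. The clustering loss is modest on assumed inputs, and the adjusted model, with race/ethnicity and doctor fixed effects, could lower it. On the denominator, Section 3.1.2 read in order suggests that the assigned patients are those with orders, and the cut to two or three arms exists to protect power: Step 3(a) shows it restores 5.5 points at 75% with three arms or 50% with two.

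Much of this stands. The 5.5 is not an arithmetic slip, nothing was concealed, and the clustering cost alone would be a minor matter. Three things remain. The logistical reason justifies sorting on surname but not a non-random map on that field. The fallback has no stated threshold, and it does not recover 5.5 points at a 25% order rate. The natural reading of Section 3.1.2 does not fit the 3,600 in Section 4.1, which counts every treatment-practice patient.

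**Conclusion.** The concern holds, as something the plan should fix; confidence is medium. The reminder comparison is non-random as described, its causal reading rests on an avoidable assumption about surnames, and the planned analysis has no variance method suited to the allocation.

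The size depends on facts the documents do not give. The denominator matters most: across the three readings, at order rates of 25% to 75% in four arms, the detectable effect runs from 3.3 points (over all patients, equal to 13.2 among those with orders) to 11.5 points. Surname clustering adds up to about half a point (6.02 against 5.53) with 200 scattered prefixes and an ICC up to 0.005. With one block per arm, the problem is bias of unknown size and direction. All these figures assume two-sided 5%, 80% power and equal arms. The randomised comparison of practices does not depend on any of this.

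**What to change.** Keep sorting on the surname field, and change the text as follows.

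- **Section 3.3:** allocate each two-letter prefix (or short prefix range, if the system needs it) to an arm with the random number generator, balanced on prefix frequency, before any message is sent. Record the map.
- **Section 4.2:** cluster standard errors for reminder comparisons on that unit, or use a permutation test over the map. Keep the race/ethnicity adjustment.
- **Section 3.4:** say whether patients without orders are in the denominator.
- **Section 4.1:** state that 5.5 points assumes 3,600 analysed patients, four arms, a 20% no-reminder rate (naming the patients it refers to) and no surname correlation. Show it over a range of order rates and surname ICCs.
- **Sections 3.1.2 and 4.1:** correct the description of the assignment as individual-level.

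The cost is a longer lookup table for sending messages and a few lines of text. If scattered prefixes cannot be sent, short ranges are the fallback at a price: with an assumed 100 units, the detectable effect is 5.7 to 6.5 points instead of 5.6 to 6.0, and chance imbalance between arms is larger.

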3.4 Endpoints/Outcomes Measurements

Hypothesis: Interfacing with primary care practices to encourage physicians to implement default online orders of blood glucose flowsheets and informational messaging for all patients with diabetes will increase patient adoption.

Outcome Measures: Comparison of individuals between treatment and control practices-- (a) fraction of patients entering blood glucose measurements into MyChart flowsheets during implementation period & follow-up period (dichotomous), (b) mean number of flowsheet entries during implementation period and follow-up period (c) fraction of patients for whom order is placed by doctor

Hypothesis: Additional reminder messaging to patients that (1) emphasizes the value of tracking blood glucose data to the patient OR (2) emphasize the value of tracking blood glucose data to the doctor OR (3) informs patient of their selection for a chance to receive an award conditional on tracking will increase adoption relative to no reminder messaging.

Outcome Measure: Comparison of individuals across reminder messaging assignment groups (within treatment practices)-- (a) fraction of patients entering blood glucose measurements into MyChart flowsheets during implementation period & follow-up period (dichotomous), (b) mean number of flowsheet entries during implementation period and follow-up period

Hypothesis: Promotion of adoption of electronic blood glucose tracking through the means described above will result in the following intent-to-treat effects:

(a) reduction in patient A1c

Outcome Measures: Intent to treat comparison of individuals between treatment and control practices of the following measures at the end of the intervention period and follow-up period: (1) Mean A1c (2) Quartiles of A1c using quantile regression analysis (3) fraction of patients experiencing improvement [reduction] in A1c from baseline (dichotomous) (4) fraction of patients below benchmark 7.0% A1c (dichotomous)

(b) increase in frequency of doctor-patient interaction

Outcome Measures: Intent to treat comparison of individuals between treatment and control practices of the following measures during the intervention period and follow-up period: (1) number of securing messaging (2) number of phone interactions, and (3) number of in-office appointments

(c) changes to treatment plan path

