Outcome Measure: Intent to treat comparison of individuals between treatment and control practices of number of alterations to patient prescriptions/medication list during the intervention period and follow-up period

Hypothesis: Reminder messaging treatments that induce more intensive use of flowsheets will lead patients to experience larger effects as described above.

Outcome Measure: Intent to treat and treatment on the treated comparison of individuals across reminder messaging assignment groups (within treatment practices)-- reduction in A1c, increase in frequency of doctor-patient interactions, changes to treatment plan path (outcomes as described above in a-c)

Hypothesis: Entries of blood glucose data will be predictive of A1c and will lower over the study period.

Outcome Measure: Descriptive analysis of flowsheet entry values in the treatment group during the implementation and follow-up period.

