4.2 Method of Data Analysis

All data analyzed in this study will be administrative health and use data that is collected as part of routine medical care and record keeping. EPIC has offered to build the SQL queries required to produce the outcome datasets described in this protocol. Outcomes listed in Section 3.4. will be analyzed using regression analysis, including (a) a version with no covariates, (b) a version controlling for patient age/gender, race/ethnicity, A1c at baseline, days since most recent office visit at baseline, and doctor fixed effects. A flag identifying patients who are eventual participants of "Impact of Innovative Interventions on Diabetic Adherence with Digital Sensors" (a study recently submitted to the IRB that may have limited overlap with this population) will also be included in the controls. For outcomes indicating analysis of practice level treatment and control groups, standard errors will be clustered at the practice level.

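### Reminder arms follow surname, the stated assumption covers adoption but not A1c, contacts or medication changes, and no check is planned although unreminded control-practice patients could supply one for those three outcomes

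*Combined protocol and SAP*

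**What the plan says.** Section 3.3: "Reminder messaging treatments will be assigned alphabetically by first two letters of patient last name". The protocol calls this pseudo-random, concedes that ethnicity may track surname spelling, and says that "the patient's race/ethnicity recorded in the medical record will be controlled for in the analysis". It then states that a causal reading of the reminder results "will thus require the assumption that grouped last name spelling is not independently related to likelihood of flowsheet adoption".

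Section 3.4 uses the surname groups twice. For adoption it specifies a "Comparison of individuals across reminder messaging assignment groups (within treatment practices"). For hypothesis 1.2.4 it specifies an "Intent to treat and treatment on the treated comparison of individuals across reminder messaging assignment groups (within treatment practices"), covering A1c, doctor-patient contacts and treatment-plan changes.

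Section 4.2 plans two regressions, "including (a) a version with no covariates", and (b) one with age/gender, race/ethnicity, baseline A1c, days since the last office visit and doctor fixed effects. It does not say which is primary.

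Section 2.2 has outcome data analyzed for the whole study population. Section 3.2 gives control practices no encouragement. Section 3.1.2 sends reminders only to "patients at treatment practices whose doctors have placed blood glucose flowsheet orders".

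**The concern.** The stated assumption is narrower than the use made of it. It excludes a link between surname group and adoption. Hypothesis 1.2.4 also needs surname group to have no link with A1c, contact frequency or medication changes other than through the reminders. Ethnicity, or anything else that varies with surname, could affect those outcomes with no flowsheet involved, and the difference would then be read as a reminder effect.

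Neither form of the assumption is checked. The plan has no balance table by surname group and no placebo comparison. Yet patients with the same surname prefixes and no study reminders sit in the control practices, with outcomes already extracted, and section 3.4 confines every reminder comparison to treatment practices.

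The treatment-on-the-treated analysis raises the stakes, because it would divide any leftover surname gap by a small adoption difference.

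**Working it through.** **Inputs.** From section 4.1: 3600 patients and 4 reminder arms; 20% adoption without reminders; 2% adoption in control practices; A1c SD 1.39; baseline correlation 0.80; within-practice ICC 0.07. Assumed here: equal groups, so 3600/4 = 900 per surname group in treatment practices and likewise in control practices; independent patients; every patient with a follow-up A1c; all treatment patients with an order; two-sided 0.05 and 80% power (multiplier 1.96 + 0.84 = 2.80). The documents give no size for any surname bias, so the values below are illustrative.

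**1. The plan's own figure.** 900 versus 900 at a 20% base gives a minimum detectable effect (MDE) of 5.53 points. The stated 5.5 reproduces, but only by treating assignment as individually random.

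**2. What a surname gap in adoption would do.** With no true reminder effect, a gap b has SE = sqrt[(0.20×0.80 + (0.20+b)(0.80−b))/900].

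| Gap (points) | Rejection rate (nominal 5%) |
|---|---|
| 1 | 8% |
| 2 | 18% |
| 3 | 34% |
| 5.5 | 80% |

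**3. Control-practice contrast for A1c.**
- Unadjusted: SE = 1.39 × sqrt(2/900) = 0.066; detectable level gap 2.80 × 0.066 = 0.18.
- Adjusted for baseline A1c: SE = 0.066 × sqrt(1 − 0.80²) = 0.039; detectable gap 2.80 × 0.039 = 0.11. This is the gap that remains after adjustment.
- The two must not be mixed. With equal variances, a stable level gap of 0.11 shrinks to 0.11 × (1 − 0.80) = 0.022 after adjustment. Then 0.022/0.039 = 0.56 standard errors, and power is about 9%.

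**4. Cost of differencing for A1c.** Subtracting one contrast from another of equal size doubles the variance, so the SE rises by sqrt(2) = 1.41. With the within-practice SD, 1.39 × sqrt(0.93) = 1.34, the adjusted MDE goes from 0.106 to 0.150. With the full SD it goes from 0.110 to 0.156.

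**5. Control-practice contrast for adoption.** Carry a bias at the 20% base to the 2% base:
- Same odds ratio: 2 points becomes 0.25 (12.5% of it); 5.5 points becomes 0.72 (13%).
- Same risk ratio: 10% of the bias in each case.
- Power to see these odds-ratio gaps with 900 per group is about 6% and 17%. A gap of 2.3 points would be needed for 80%.
- Subtracting the control contrast raises the adoption MDE from 5.53 to 5.84 points.

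**6. Treatment on the treated.** If this is the usual ratio estimator (the protocol does not say) and adoption differs by 5.5 points, a direct surname gap is multiplied by 1/0.055 = 18. A 0.05 A1c gap becomes about 0.9. Even the 0.022 left in step 3 becomes 0.022/0.055 = 0.4.

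**The case against.** Section 3.3 discloses the assumption, names the likely route of bias and commits to adjusting for it. Version (b) goes further: baseline A1c is the covariate that matters most for the A1c comparison and, under the plan's own correlation, cuts a stable gap to about one fifth. Section 1.1 also makes the health analyses conditional on a significant rise in adoption. All of this stands. It does not cover version (a), supplies no test, and leaves contacts and medication changes without baseline counts among the covariates.

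A reader might infer that the control practices would both test and remove surname bias at no cost. The documents do not support that, for three reasons.
- For adoption, entries need a physician order, which section 1.3 says is rarely placed. A surname effect on use is nearly invisible at 2%.
- For the health outcomes, differencing replaces one assumption with another. Treatment practices also receive batch orders, alerts and a physician message (section 3.1.1). If response to that promotion varies with surname, the difference is still charged to the reminders. Surname gaps must also be equal in the two sets of practices.
- Precision is lost, as step 4 shows.

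Running unadjusted and adjusted models side by side is ordinary practice. The point is only that section 4.2 does not say which one leads, while section 3.3 promises adjustment.

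**Conclusion.** The concern holds as a gap in identification and checking. Surname assignment is carried over to A1c, contacts and medication changes under an assumption written for adoption, and an available falsification test is unused.

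For A1c the test is informative: a pre-existing level gap of about 0.18 is detectable with 80% power. The figure of 0.11 applies only to a gap remaining after baseline adjustment. Contacts and medication changes are also recorded without a flowsheet order, so the test should be usable there, but the documents give no variances from which to size it. For adoption it is a weak check, showing roughly 10-13% of a proportional bias; a null result gives no reassurance.

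It would be too strong to infer that the reminder results are biased: the documents show the route, not a bias or its size. The figures rest on the equal groups, patient independence and complete A1c follow-up listed above. A1c comes from routine care only, so fewer measurements, or shared effects within letter pairs, would widen the standard errors.

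**What to change.** 1. Fix the letter-pair-to-arm map in advance. Derive the surname-group code (no name) for all patients, control practices included, before identifiers are removed for the limited dataset (section 4.3).
2. Restate the section 3.3 assumption to cover every outcome compared across reminder groups.
3. Pre-specify the surname-group contrast in control practices as a falsification test for A1c, contacts and medication changes, with a baseline balance table by surname group.
4. For hypothesis 1.2.4, report the treatment-minus-control differenced estimate as a sensitivity analysis. Group all treatment-practice patients by surname code, or state the mismatch with the order-only reminder population. State that it assumes equal surname gaps in both sets of practices and no surname-related response to practice-level promotion.
5. Make version (b) the main model for reminder comparisons, with version (a) as sensitivity.
6. For adoption, report the control contrast only as a weak check, with its limits.

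Cost: one derived variable, one interaction term and one table, with no change to care or messaging. The differenced estimate has an SE about 1.4 times larger (adjusted A1c MDE about 0.15 instead of 0.11), which is why it should not be primary.
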